## **Aim**

The aim of this study is to investigate the effect of a single preoperative high-dose steroid injection on complications in the immediate postoperative phase after breast cancer surgery, with removal of the breast (mastectomy). Primary outcome is the proportion patients who require transfer to the post anesthesia care unit (PACU) and the proportion that can be transferred directly to the ward. Secondary outcomes are organ specific complications in the post anesthesia phase, pain and nausea the first 5 days, seroma and wound infection the first 14 days and readmissions the first 30 days after surgery.

The investigators hypothesize that the frequency of transfer to the PACU and organ specific complications will be lower among patients receiving high dose dexamethasone. The investigators hypothesize, that there will be no difference in wound infections, seroma or readmissions.

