### **Secondary outcomes**

- Discharge score in the operating room (according to discharge criteria, Appendix 1).
- Discharge score at arrival to the ward or PACU (according to discharge criteria, Appendix 1).
- Complications/adverse events in the ward the first 24 h or until discharge.
- Length of stay (PACU/Hospital)
- Pain, self-reported in patient questionnaire. Days 0-4.
- Nausea/vomiting, self-reported in patient questionnaire. Days 0-4.
- Analgetics and antiemetics, use of, self-reported in patient questionnaire. Days 0-4.
- Quality of sleep, self-reported in patient questionnaire. Days 0-4.
- Feelings of anxiety, restlessness, fatigue, self-reported in patient questionnaire. Days 0-4.
- Seroma, requiring drainage, the first 14 postoperative days

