### **Post-operative treatment**

Analgesics: By request, acetaminophen 1 g up to 4 times daily, ibuprofen 400 mg up to three times daily, from the evening of surgery up to and including the fifth postoperative day.. Opioids are only given in hospital, on request based on moderate or severe pain.

Antiemetics: By request, or if vomiting occurs.

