### **Clinical evaluations and outcome registration**

Pain (at rest) is evaluated on a numeric rating scale (NRS) by the patient, assigning pain a number between 0-10. Study personnel assign a score according to the criteria listed in appendix 1, where NRS 0 = 0 (no pain),  $0 < \text{NRS} \leq 3 = 1$  (light pain),  $3 < \text{NRS} < 7 = 2$  (moderate pain),  $\text{NRS} \geq 7 = 3$  (severe pain). If patients are not able to assign a number (e.g. due to sedation/doubt), it is accepted with a verbal rating scale (no/light/moderate/severe pain).

Nausea is evaluated by patients and assigned a score from 0 (no nausea) to 3 (severe nausea or vomiting).

Length of stay (hospital) is measured as time (hours and minutes) from start of the procedure until discharge from the ward.

Length of stay (PACU) is measured as time from arrival to PACU until the patient is deemed ready to transfer to the ward (as the actual transfer time depends on transport etc.).

The occurrence of seroma requiring drainage is recorded the first 14 postoperative days from patient records.

Readmissions for any reason, except planned procedures or oncological admissions, are collected from patient records for 30 days.

Side-effects and/or complications (any) are registered during hospital stay and up to 60 hours postoperatively. Adverse events/serious adverse events are defined according to ICH-GCP.

Patients receive a questionnaire to fill out on days 0-4. The elements of the questionnaire are:

- pain on average and at worst on the 11-point numeric rating scale (0 no pain, and 10 worst pain imaginable)
- nausea on average and at worst on the four-point numeric scale (0, none; 1, slight; 2, moderate; 3, severe) and vomiting (if any)

- use of analgesics
- feelings of sadness, restlessness or fatigue (yes/no)
- quality of sleep (good, difficulty falling asleep, frequent awakenings, no sleep)

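### General safety events are registered only during the hospital stay and up to 60 hours, and the plan states no serious-event window or assessment rule to match its own 30-day readmission follow-up

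*Combined protocol and SAP*

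**What the plan says.** Four statements bear on this point.

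- **General registration.** Protocol, Clinical evaluations and outcome registration: "Side-effects and/or complications (any) are registered during hospital stay and up to 60 hours postoperatively". The next sentence reads "Adverse events/serious adverse events are defined according to ICH-GCP". It gives a definition, but no period, assessor or reporting route.
- **A second window.** Protocol, Secondary outcomes: "Complications/adverse events in the ward the first 24 h or until discharge".
- **Late outcomes.** The Aim lists "seroma and wound infection the first 14 days and readmissions the first 30 days after surgery". Clinical evaluations and outcome registration adds "The occurrence of seroma requiring drainage is recorded the first 14 postoperative days from patient records" and "Readmissions for any reason, except planned procedures or oncological admissions, are collected from patient records for 30 days".
- **Analysis.** The Statistical Analysis Plan compares seroma drainage, readmissions and wound infections between the groups by chi-square test. It specifies no analysis or table of adverse or serious adverse events.

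The Blinding section names a data monitoring committee. The Data management section provides for approval by the medicines agency and monitoring by the Good Clinical Practice unit. Neither says which safety events reach whom, or when.

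**The concern.** The trial compares a higher with a lower single steroid dose and expects no difference in wound infection, seroma or readmission. Those outcomes are followed for two to four weeks. The only general rule for recording harm stops at 60 hours, or at discharge if the stay is longer.

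Two things are at stake. First, a late readmission enters the data as a count, without a stated judgement on whether it was serious or related to the trial drug. Second, some late serious events fit none of the named outcomes, so under the written rule nobody has to record them. A statement on the safety of the higher dose would then rest on three named late outcomes plus a short general record, and events outside those would be missing by rule. The primary outcome is not affected.

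**Working it through.** The plan gives no figure on this point, and the sample size of 130 does not enter. The check sets the windows side by side and then follows example events through them.

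**Windows, counted from surgery**

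| Item | Window | Source |
|---|---|---|
| Ward complications/adverse events | 24 h or until discharge | Secondary outcomes |
| Side-effects and complications, any kind | hospital stay and up to 60 h | Clinical evaluations |
| Seroma needing drainage | 14 days | Clinical evaluations; Aim |
| Wound infection | 14 days | Aim |
| Readmissions | 30 days | Clinical evaluations; Aim |
| Adverse/serious adverse events | definition only | Clinical evaluations |

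**Time without general registration**, taking discharge by 60 h:

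- 60 / 24 = 2.5 days.
- To day 14: 14 × 24 − 60 = 336 − 60 = 276 h, or 11.5 days.
- To day 30: 30 × 24 − 60 = 720 − 60 = 660 h, or 27.5 days.

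These are lengths of time. They do not measure missed events, because events need not be spread evenly over the period.

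**Example events**, in a patient discharged at 30 h:

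1. *Side-effect at home at 48 h.* Inside the 60-hour window, outside the ward window. The two sections give different answers unless the ward outcome is meant as a subset of the 60-hour record, which is not stated.
2. *Seroma drained on day 10.* Recorded and compared between arms.
3. *Wound infection on day 10.* Named in the Aim and tested in the analysis plan. The section on clinical evaluations gives collection rules for seroma and readmissions, but none for wound infection.
4. *Unplanned, non-oncological readmission on day 7.* Recorded and compared between arms. No rule for assessing seriousness or causality, or for reporting it.
5. *Unplanned oncological admission on day 7.* Excluded from the readmission outcome and past 60 h, so no place of record.
6. *Death at home on day 12.* Not a readmission and past 60 h, so no place of record.
7. *Other serious event on day 12, treated without admission.* No place of record, unless it is a drained seroma or a wound infection.

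Event 1 shows the mismatch between the two windows, event 4 the missing assessment rule, and events 5 to 7 the gap in capture.

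**The case against.** The strongest reply is that the 60-hour limit is written for side-effects and complications. The sentence on adverse and serious adverse events gives only a definition, so a 60-hour cut-off for serious events is a reading and not a stated rule. That is fair. But if the limit does not apply to serious events, the plan states no window for them at all, and the remedy is the same.

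A reader might go further and infer that late events are never assessed, or that nothing reaches the sponsor or the committee. The documents do not support this. They are silent on it, and they do provide for Good Clinical Practice monitoring and a data monitoring committee. What can be said is that no rule is stated.

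A reader might also infer that late harm goes unmeasured. It does not: seroma, wound infection and readmissions are collected past 60 hours and compared between arms. Nor can one say that a serious-event table would contradict the readmission table, since the analysis plan contains no serious-event table.

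Finally, it is tempting to argue that registration ends while patients may still take analgesics up to day 5. This adds little. The trial drug is a single dose, and the day-5 limit belongs to on-request analgesics offered to both arms.

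What remains after these concessions is the mismatch between windows, the missing rule for assessing and reporting readmissions, and the events with no place of record.

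**Conclusion.** The point holds as a gap in safety capture and reporting. It changes neither the sample size, the power, the significance level nor any planned comparison.

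In time, the gap is up to 11.5 days before the end of the 14-day outcomes and up to 27.5 days before the end of the readmission window. It is shorter for a patient whose hospital stay exceeds 60 hours. The number of affected patients is unknown, because the documents give neither a readmission risk nor a late serious-event risk.

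The conclusion rests on three assumptions:

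- The 60-hour rule is the only one for general safety events, as far as the available text shows.
- The hospital stay extends the window where it is longer. If 60 hours is instead a cap, the gap is the same for patients discharged earlier and larger for those who stay longer.
- The exception to the readmission outcome covers all oncological admissions. If only planned ones are meant, unplanned ones are already counted as readmissions, and event 5 joins event 4.

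The documents cite the ICH-GCP definition without reproducing it. The fix therefore names deaths and unplanned admissions outright and does not depend on how that definition is read.

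**What to change.** 1. Reconcile Secondary outcomes with Clinical evaluations and outcome registration. Either give one window for complications and adverse events, or state that the ward outcome is a subset of the 60-hour record.
2. Keep a short window for non-serious side-effects.
3. Add to Clinical evaluations and outcome registration: *Serious adverse events, including death and unplanned admission of any cause, are registered to day 30 from the record review carried out for readmissions. The blinded investigator assesses each for seriousness and causality and reports it to the sponsor and the data monitoring committee.*
4. Add to the Statistical Analysis Plan a descriptive table of serious adverse events to day 30 by arm, using coded arms until the allocation is revealed. No further test is needed.

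**Cost.** The change needs a few sentences of protocol and analysis-plan wording, and a form for each late serious event, some of which will be unrelated to the trial drug. The record review to day 30 is already planned, but it must also note deaths, serious events without admission and unplanned oncological admissions. The readmission outcome can keep its present definition. No extra visit or procedure is needed.

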#### **Other collected data**

Demographical data (sex, age, height, weight, smoking status, use of alcohol, comorbidities), operative data (date and time of operation, diagnosis, duration of surgery, extent of axillary dissection, intraoperative bleeding). Type and dose of medication given by request.

All data are collected from patient record.

#### **Sample size**

After modification of our ERAS protocol introducing high-dose glucocorticoids (125 mg methylprednisolone (equivalent to 24 mg dexamethasone) we observed a 30 % to 10 % decrease in PACU referral after mastectomy. To test the isolated effect of the increased glucocorticoid dosage in a well-implemented ERAS protocol, we chose to compare 24 vs 8 mg dexamethasone. Considering the observed 20 % absolute (66% relative) reduction in need for PACU transfer clinically relevant, a sample size of 130 patients (65 in each group) was calculated ([www.sealedenvelope.com](http://www.sealedenvelope.com)) with a two-sided 5 % significance level, a power of 80 % and an anticipated 10 % exclusion rate.

## Appendix 1. Danish Society of Anesthesiology and Intensive Care Medicine (DASAIM)-score, modified.

Modifications: Pain score is numeric rating scale 0-10 instead of Visual analogue scale 0-100 mm. Oxygen saturation was measured with 2L supplementary oxygen in the operating room. Respiratory rate as category is omitted.

Patients are considered dischargeable to the ward when the score sum of all criteria is four or less and no single score is above one.

Modality	Score	Criteria
Sedation (nurse evaluation)	3	Sleeping, cannot be aroused
	2	Sleeping, aroused by physical stimuli
	1	Sleeping, aroused by verbal stimuli
	0	Fully awake
Oxygen saturation; %	3	< 85
	2	85-89
	1	90-93
	0	≥ 94
Blood pressure, systolic (mmHg) (automatic NIBP)	3	< 80
	2	80-89 or > 220
	1	90-99
	0	100-220
Heart rate; pr. min. (automatically derived from ECG)	3	< 40 or > 130
	2	40-49 or 121-130
	1	101-120
	0	50-100
Pain (at rest) Numeric Rating Scale (NRS) 0-10 (patient evaluation)	3	Severe (NRS ≥ 7)
	2	Moderate (3 ≤ NRS < 7)
	1	Light (0 < NRS < 3)
	0	None (NRS = 0)
Nausea (patient evaluation and nurse observation)	3	Severe
	2	Moderate
	1	Light
	0	None
Total	Sum
